#### **6.5.6. *Classification of Patients at Termination of Treatment***

To provide for consistent accounting of patient disposition, when study treatment is discontinued in an individual patient for any reason, the Investigator will complete the appropriate electronic case report form (eCRF) and select the primary reason from the following standard categories:

- *DLT event* – defined above.
- *Disease progression* – as defined above.
- *Adverse Event, other than DLT* – This includes any AE (clinical or laboratory; serious or non-serious; regardless of relation to study drug), that represents the reason study drug was discontinued, including:
  - The medical judgment of the Investigator based on the best interests of the patient.
  - The patient's request based on any AE.
- *Withdrawal of Consent* – The patient desired to withdraw from further participation in the study in the absence of a clinical issue. If the patient gave a reason for withdrawing (e.g., leaving area), it should be recorded in the eCRF.
- *Lost to Follow-Up* – The patient stopped coming for visits.
- *Study Termination* – by the Sponsor, for any reason.

When study treatment is discontinued for any reason, the End-of-Treatment (EOT) and End-of-Study (EOS) visits will be performed as specified (see [Section 1.4](#)). If a patient cannot be seen, attempts will be made to contact the patient by telephone to inquire about reasons for stopping participation and get updated information on any unresolved AEs.

### **6.6. *Criteria for Replacement Patients***

#### **6.6.1. *Definition of a Evaluable Patient***

A patient will be considered evaluable for purposes of DRC review if they meet *either* of the following criteria:

- Received at least 1 dose of study drug and had treatment discontinued because of a DLT event as defined in [Section 6.3.1](#); or
- Received all doses of study drug in the first 4 weeks of treatment and completed Week 5 assessment procedures.

See [Section 12](#) for additional discussion of analysis for safety and efficacy.

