## 6.5. Management of Individual Patients

### 6.5.1. Duration of Treatment

Each enrolled patient will receive IMO-8400 at the assigned dose level until the earliest of:

- *Clinical DLT event* – see [Section 6.3](#).
  - Study treatment will be discontinued in patients determined to have a clinical DLT event until resolution and may only be resumed after discussion with an Idera Medical Monitor and agreement that it is in the patient's best interest to continue.
  - For a DME, provision is made for interrupting dosing for up to 3 weeks and, if the acute toxicity improves sufficiently, resuming treatment at a lower dose level based on discussion between the sponsor's designated medical monitor and the treating physician.
  - For DLT laboratory events, provision is made for pausing treatment for up to 3 weeks and, if the acute toxicity improves sufficiently, resuming treatment at a lower dose level (see [Section 6.5.2](#) for details).
  - The Investigator will review with the Medical Monitor decisions to discontinue, pause, and/or restart study treatment.
- *Disease progression* – based on scheduled assessments at Week 1 of each cycle. Unscheduled assessments may be conducted in response to new clinical observations. Disease status will be classified according to international guidelines [1] (see [Section 9.5](#) for details).
- *Termination of participation in the study* – due to AE, withdrawal of consent, intolerable toxicity, or loss to follow up.

In certain instances, patients may be deriving clinical benefit despite objective signs of progressive disease such as radiologic progression. It can be anticipated that based on the study drug's mechanism of action, through an immunologic mediated effect, signs of radiologic response may be delayed. Based on these considerations, continuing to treat some patients past progressive disease may be considered after discussion between the Sponsor and Investigator, provided the following conditions are met:

- Patient has not achieved an objective response on study and then developed progressive disease;

- Patient has not experienced a period of clinically significant stable disease on study and then developed progressive disease;
- Patient must be re-evaluated 4 to 6 weeks after initial progression in order to confirm progressive WM disease;
- If the follow-up assessment does not confirm progressive disease, patient may resume regularly scheduled follow-up per protocol;

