#### **6.6.2. *Replacement Patients***

A patient who does not meet criteria for “evaluable” may be replaced to assure the requirements for completing the cohort are met. Replacement patients will be identified by distinctive patient numbers and will receive the same dose level as the patient being replaced.

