#### **10.4.6. Management of Study Drug upon Occurrence of an Adverse Event**

For each AE the Investigator will indicate which one of the following actions regarding the administration of study drug was taken because of that AE:

- **Discontinued (withdrawn)** — study drug was stopped permanently due to the AE.
- **Dosing Interrupted** — study drug regimen was modified by being temporarily halted, i.e., 1 or more doses were not administered, but drug was not stopped permanently.
- **Dose Decreased** — study drug regimen was modified by subtraction, i.e., by decreasing the frequency, strength or amount.
- **None** — no change in the administration of study mediation.

For patients whose treatment is paused and then resumed at a lower dose level as detailed in [Section 6.5.2](#), the management of study drug will be recorded as “Dose Decreased.”

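### Section 6.6.1 can class a patient with a paused and resumed laboratory DLT as non-evaluable and replaceable, although Sections 6.3.2 and 6.3.3 count that patient

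*Protocol*

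**What the plan says.** Section 6.6.1 defines who is evaluable for DRC review. A patient qualifies by either route:

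- Route 1: "Received at least 1 dose of study drug and had treatment discontinued because of a DLT event".
- Route 2: "Received all doses of study drug in the first 4 weeks of treatment and completed Week 5 assessment procedures".

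Under Section 6.6.2, a patient who meets neither route "may be replaced to assure the requirements for completing the cohort are met".

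How treatment is handled after a DLT depends on its type (Section 6.5.1):

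- Laboratory: "For DLT laboratory events, provision is made for pausing treatment for up to 3 weeks", after which treatment may resume at a lower level. Section 6.5.2 sets the conditions, including recovery within 14 days of the last dose. It excludes patients at 0.6 mg/kg/week, who are discontinued.
- Clinical: "Study treatment will be discontinued in patients determined to have a clinical DLT event until resolution and may only be resumed after discussion".

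The counting rules sit elsewhere. Section 6.3.2 defines the MTD, and Section 6.3.3 the cohort decisions, by the number of patients who experienced a DLT in the first 4 weeks. Neither mentions evaluability or whether treatment stopped. Sections 1.3.5 and 6.3.3 have the DRC review all safety data.

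**The concern.** Route 1 turns on what happened to treatment, not on whether a DLT occurred. A patient whose DLT led to a pause and a restart, with a dose missed on the way, is therefore labelled non-evaluable for the review that sets the MTD. That patient may be replaced, while the counting rule still includes the patient. No passage says that a patient with a DLT is always evaluable or may not be replaced.

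Safety is the primary objective and each escalation decision rests on 3 to 6 patients, so the status of one patient can decide it. If someone takes the replacement rule to remove the patient from the cohort under review, the DLT count falls by one. That error can run only toward escalation.

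**Working it through.** **1. Does a paused laboratory DLT meet route 1?** The uses of the word in the protocol point to no.

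- Section 6.3.1 (last bullet) and Section 6.5.1 name pausing and discontinuing as separate actions.
- Section 6.5.6, directly before 6.6.1, uses the word for the end of treatment: "When study treatment is discontinued for any reason, the End-of-Treatment (EOT) and End-of-Study (EOS) visits will be performed as specified".
- Section 10.4.6 defines Discontinued as "study drug was stopped permanently due to the AE". It records a patient who is paused and then resumed at a lower level under 6.5.2 as Dose Decreased.

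So the protocol's own coding puts this patient outside route 1.

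**2. Can a dose in the first 4 weeks be missed, so that route 2 fails too?** Inputs:

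- Focused panel before the Week 3 dose (Table 4, footnote 14): Day 15.
- Results within 48 hours (9.7.2): Day 15 + 2 = Day 17.
- Recovery limit (6.5.2), with last dose on Day 15: 15 + 14 = Day 29.
- Three-week pause, taken from the last dose: 15 + 21 = Day 36.
- End of the first 4 weeks: Day 28.

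*Once weekly* (Days 1, 8, 15, 22; a reduced dose is taken to count as a dose):

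| Recovery | Doses by Day 28 | Evaluable? |
|---|---|---|
| By Day 24 (22 + 2, the 8.4.2 allowance) | 4 of 4 possible | Yes, route 2 |
| Days 25 to 28, next dose as soon as feasible (8.4.2) | 4 of 4 still possible | Yes, if given by Day 28 |
| By Day 29, restart on Days 29 to 36 | 3 of 4 | Neither route |
| Not by Day 29 | 3 of 4 | 6.5.2 not met; route 1 plausibly applies |

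The exposed case is recovery at about Days 28 to 29, or a delayed restart.

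*Twice weekly, Dose Level 3* (Days 1, 4/5, 8, 11/12, 15, 18/19, 22, 25/26): 5 of 8 injections are given by Day 17, and the next is due on Day 18 or 19. Section 6.5.2 resumes dosing at the next lower level, which in Table-8 is once weekly. With a restart on Day r ≥ 17, the next doses fall on r + 7 and r + 14. Even 2 days early, the third falls no sooner than 17 + 14 − 2 = Day 29. So at most 2 further doses fall by Day 28, giving 5 + 2 = 7 of the original 8. Any pause and restart under 6.5.2 from this point therefore misses route 2, unless "Received all doses of study drug in the first 4 weeks of treatment and completed Week 5 assessment procedures" is measured against the reduced schedule, which the text does not say.

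**3. What if one DLT is dropped and the replacement has none?** Applying 6.3.2 and 6.3.3:

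| True count | Read as | Outcome |
|---|---|---|
| 1/3 | 0/3 | Changes: escalation review instead of enrolling to 6 |
| 2/3 | 1/3 | Changes: enrol to 6 instead of halting for review |
| 3/3 | 2/3 | Unchanged: still halts |
| 1/6 | 0/6 | Unchanged |
| 2/6 | 1/6 | Changes: the level can qualify as the MTD |
| 3/6 or more | one fewer | Unchanged |

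**4. Cases not affected.** Laboratory DLTs at 0.6 mg/kg/week are discontinued (6.5.2) and meet route 1. A DLT first found at Week 5 after full dosing meets route 2.

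**5. Plausibility.** Section 4.4.1 reports related Grade 3 anemia, a laboratory finding that 6.3.1 does not exempt; its timing is not given. The one DLT reported there was clinical.

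**The case against.** The best reply is that the two rules answer different questions. Section 6.6.2 is about completing a cohort. The DLT count in 6.3.2 and 6.3.3 is in absolute numbers of patients and never uses the word evaluable. On that text, replacing a patient erases nothing and adds one more patient at risk of a DLT, which is conservative. This stands: a reader might infer that the protocol removes such DLTs from the count, and it does not. What remains is that 6.6.1 states its purpose as DRC review, so it invites the reading that a non-evaluable patient is outside that review.

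A reader might also infer that every DLT without discontinuation makes a patient non-evaluable. Route 2 contradicts that: a patient with a DLT, full dosing and the Week 5 assessments is evaluable.

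Nor can the point be extended firmly to clinical DLTs. Section 6.5.1 uses the word discontinued for a stop that lasts until resolution, so a clinical DLT that is later resumed plausibly meets route 1. Section 10.4.6 points the other way, since it keeps a temporary halt ("1 or more doses were not administered, but drug was not stopped permanently") in its own category, but those are recording categories for adverse events. The wording is ambiguous there, no more.

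The conditions also narrow the case. The laboratory event must be confirmed and assessed as related (6.3.1), and both the Investigator and the Medical Monitor must support continuing. Replacement is optional. The DRC Charter, which is not shown, may settle the matter; the protocol should still agree with itself.

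**Conclusion.** The first route in 6.6.1 is wrong as written. A laboratory DLT above 0.6 mg/kg/week that is paused and resumed, with a first-4-week dose missed, meets neither route and may be replaced, although 6.3.2 and 6.3.3 count it. The literal count is unbiased. The defect is an inconsistency that permits a reading in which a DLT disappears, always toward escalation, and which would change the outcome at 1/3, 2/3 and 2/6.

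Exposure is easiest at the twice-weekly level and narrow at once-weekly levels. The timing assumes that the event is found on the scheduled Week 3 panel and that dosing is otherwise on schedule.

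A reader might want a probability of wrong escalation. None can be derived: it would need the true DLT rate and the share of DLTs that are paused and then dropped, and the protocol gives neither.

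**What to change.** - **Section 6.6.1, first route:** reword to *received at least 1 dose and experienced a DLT event in the DLT assessment window, whether treatment was stopped, paused or resumed*.
- **Section 6.6.2:** add that such a patient stays in the DLT count and is not replaced.
- **DLT window:** reconcile the first 5 weeks in 6.3.1 with the first 4 weeks in 6.3.2 and 6.3.3, so that the reworded criterion has one meaning.
- **DRC Charter:** align it with the result.

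The cost is one reworded criterion, one sentence and the alignment of the window and Charter. There are no new visits or procedures. The rewording changes counting only, not any dose or management rule.

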#### **6.6.2. *Replacement Patients***

A patient who does not meet criteria for “evaluable” may be replaced to assure the requirements for completing the cohort are met. Replacement patients will be identified by distinctive patient numbers and will receive the same dose level as the patient being replaced.

## **6.7. Maximum Number of Patients and Maximum Exposures**

The maximum exposures to IMO-8400, the investigational agent in this study, will be as follows:

- Maximum number of patients: Approximately 60 patients in planned escalation and expansion cohorts; potential for additional patients in contingency cohorts or as replacements.
- Maximum dose level: Undefined (pending dose escalation results). The planned dose escalation cohort levels for IMO-8400 are 0.6, 1.2, 2.4, and 3.6 mg/kg administered once weekly and 1.2 mg/kg administered twice weekly
- Maximum duration of exposure: undefined (treatment is until study completion or until the patient experiences intolerable toxicity, disease progression, or withdraws consent, whichever comes first as defined in [Section 6.10.2.2](#)).

## **6.8. Treatment Assignment**

See [Section 9.3](#).

## **6.9. Criteria for Study Termination**

The study ends approximately 6 months following enrollment of the last patient. The Sponsor reserves the right to discontinue or suspend the study earlier for safety or administrative reasons at any time, at an individual site or overall. Should the study be terminated and/or the site closed for whatever reason, all study documentation must be archived and study medication must be destroyed according to local policy or returned to the Sponsor or its representative per Sponsor's instructions.

If the trial is terminated prematurely or suspended, the Sponsor will promptly inform the participating Investigators and institutions, the regulatory authorities, and the Institutional Review Board (IRB) of the termination or suspension and the reason(s) for the action.

## **6.10. Discussion of Study Design and Treatment Regimens**

This protocol represents the first clinical trial of IMO-8400 in patients with B-cell malignancies and the third clinical trial of IMO-8400 overall.

### ***6.10.1. Rationale for Study Structure***

The open-label study design is consistent with both the study objectives and current principles for the evaluation of investigational drugs in patients with advanced malignancy.

The dose escalation design with enrollment guided by safety experience and reviewed by a DRC are standard for a Phase 1 study and serve to minimize the number of patients required and to assure patient safety is protected.

The expansion cohorts will permit preliminary signal-seeking and guide further development of IMO-8400 in oncology/hematology.

## ***6.10.2. Rationale for Treatment Regimens in Current Protocol***

### **6.10.2.1. Dosing Regimen**

**Starting dose/Safety.** The proposed starting dose (0.6 mg/kg/week) is consistent with the safety experience in protocol 8400-001, the Phase 1 study, in which that dose was administered for 4 weeks without incident to healthy volunteers; and in protocol 8400-201, the Phase 2a study, in which that dose was administered for 12 weeks to patients with moderate to severe plaque psoriasis. The primary TEAEs observed were mild injection sites reactions; there were no treatment-related changes in laboratory studies, including tests of liver and renal function.

**Dosing interval.** Once and twice weekly dosing are supported by animal studies of autoimmune diseases and in vivo tumor growth.

**Dose escalation.** Numerically larger increases in hemoglobin and a faster time to response were seen in patients dosed at the highest dose level studied in the current trial [24]. In the absence of dose-limiting toxicity, further dose escalation to determine the extent of disease control that can be attained is appropriate and consistent with standard oncology Phase 1 trial design.

### **6.10.2.2. Duration of Treatment**

Treatment with IMO-8400 will continue until study completion or until the patient experiences intolerable toxicity, disease progression, or withdraws consent, whichever comes first.

**Follow-Up.** Additionally, patients who have discontinued study treatment for reasons other than progressive disease will be assessed per Response Assessment in WM from the VIth International Workshop, at a minimum of every 12 weeks ( $\pm$  4 weeks) until documentation of progressive disease, start of new anti-cancer therapy, or until study completion, for up to 6 months from the last patient's first treatment (Cycle 1, Day 1), whichever comes first.

## 7. SELECTION OF PATIENTS

### 7.1. Source of Patients and Recruitment Methods

Following receipt of IRB approval, the Investigator may initiate patient recruitment (see [Section 13](#)). To reach an economically and socially diverse population, the study may be announced in newspapers and on relevant Internet websites; prior to use, the form and content of such announcements will be submitted to the IRB for approval (see [Section 13](#)).

### 7.2. Patient Restrictions during the Conduct of the Study

In the interest of their safety and to facilitate assessment of both safety and treatment effect, the patients participating in this study will be requested to agree to the following restrictions during the study:

- Not start any new prescription medications, except as prescribed or approved by their Investigator or if required in an emergency;
- Not take any over-the-counter medications, except as instructed or approved by their Investigator.

## 8. STUDY TREATMENT

### 8.1. Study Treatments to be Administered

All patients will receive the investigational study drug, IMO-8400, at the weekly exposure level designated for the cohort in which they are enrolled. Instructions for dose preparation are provided in the Pharmacy Manual. Weekly exposure levels are calculated as mg/kg based on body weight at Screening. The dose is to be recalculated if change in body weight from Screening exceeds 10% ( $\pm$ ). Dose volume per injection site should not exceed 1.2 mL/site, with multiple sites used per dose as necessary.

### 8.2. Description and Manufacture of Study Drug

All manufacture, packaging and labeling operations will be performed according to Good Manufacturing Practice (GMP) and Good Clinical Practice (GCP) guidelines, as well as US regulations.

**Table-9. Physical and Chemical Properties of Active Ingredient (Drug Substance)**

Name	IMO-8400
Drug Class	Oligonucleotide antagonist of TLRs 7, 8 and 9
INN	NA
Molecular Formula	$C_{179}H_{216}N_{52}Na_{17}O_{101}P_{17}S_{17}$ (sodium salt)
Molecular Weight	6174 (sodium salt)
Appearance	hygroscopic white to off-white amorphous solid obtained by lyophilization
Solubility	freely soluble in aqueous media
Melting Point	amorphous powder, decomposes without a defined melting point.

Abbreviations: INN=international nonproprietary name; NA=not applicable; TLR=Toll-like receptor

**Table-10. Formulation of IMO-8400 for Injection (Drug Product)**

Name	IMO-8400 for Injection, 150 mg
Active ingredient	IMO-8400
Excipients	Each vial contains nitrogen (National Formulary).
How supplied	Sterile, lyophilized powder for reconstitution packaged in a clear, round 5-mL glass vial with a rubber stopper and aluminum overseal. Each vial contains 150 mg IMO-8400 free acid, as labeled, corrected for moisture and impurities.
Storage	The sealed vials of formulated drug product should be stored at 2-8°C.
Preparation and handling	Vials are reconstituted using Sterile Saline or Sterile Water for Injection, USP (to be provided by study site). The choice of diluent and the reconstitution volume are determined by the vial strength and the dose level assigned; see Pharmacy Manual for details.
Administration	The dose is administered as SC injection(s), not to exceed 1.2 mL/site, with multiple sites used per dose as necessary, using a fresh sterile needle (approximately 26 g); see Section 8.4 regarding the site of injection.

Abbreviations: SC=subcutaneous; USP=United States Pharmacopeia

### 8.3. Reconstitution of IMO-8400 for Injection

Detailed dose-preparation instruction and flow-sheets are provided in the Pharmacy Manual.

## **8.4. Administration of Study Treatments**

Each dose of IMO-8400 will be administered as SC injection(s), not to exceed 1.2 mL/site, with multiple sites used per dose as necessary. For example, a 1.5 mL dose volume would be administered as two separate injections of 0.75 mL. The injection sites should be selected based on the following:

- Areas for injection are the 4 quadrants of the abdomen (upper and lower on the left and right) and the upper thigh of each leg.
- Injection sites should be rotated, that is, no injection area used more than once every 6 injections.

In the event these guidelines cannot be accommodated due to injury or other issue, the Investigator should discuss the situation with the Idera Medical Monitor.

### **8.4.1. Pre-Treatment Criteria**

IMO-8400 should not be administered until the following conditions are met:

- Hemoglobin  $\geq 7.5$  g/dL
- ANC  $\geq 1,000/\mu\text{L}$
- Platelets  $\geq 50,000/\mu\text{L}$
- All other laboratory abnormalities to baseline or grade  $\leq 1$

These parameters will be measured at local laboratories at Week 1 and Week 5 of each cycle.

### **8.4.2. Variances in Dose Administration Schedule**

**Once weekly dosing:** for patients assigned to dose levels of 0.6, 1.2, 2.4, or 3.6 mg/kg/week. The expectation is that patients will be dosed each week on the same day of the week. To allow for holidays and other scheduling issues, individual doses may be administered up to 2 calendar days earlier or later than expected, while remaining on the same schedule. Doses should not be administered fewer than 5 calendar days after the preceding dose.

If, for any reason (e.g., scheduling or toxicity), dosing is interrupted more than 2 calendar days beyond expected, then the next dose should be administered as soon as feasible and the schedule reset to once weekly on the next convenient weekday.

**Twice weekly dosing:** for patients assigned to the dose level of 1.2 mg/kg twice weekly (2.4 mg/kg/week). The total weekly exposure will be administered as a 2 separate SC injections of 1.2 mg/kg per injection, respectively, over the course of the week. The expectation is that patients will be dosed twice each week on the same day of the week, with (approximately) 72 or 96 hours (3 or 4 calendar days, respectively) between injections. The minimum interval between successive doses may not be less than 48 hours (2 calendar days). If, for any reason (e.g., scheduling or toxicity), the interval between successive doses is 6 or more calendar days, then the next dose should be administered as soon as feasible and the twice weekly dosing schedule resumed.

**Extended dosing interruptions.** If, for any reason, dosing is interrupted for more than 21 calendar days due to toxicity, the patient should be discontinued from study treatment unless

the Investigator and the Idera Medical Monitor agree that it is in the patient's best interest to continue.

